1.3.2 MRI Risk

MRI uses a magnet and radio waves to make diagnostic medical images of the body. There have been no ill effects reported from exposure to the magnetism or radio waves used in this test. However, it is possible that harmful effects could be recognized in the future. A known risk is that the magnet could attract certain kinds of metal. Therefore, the technologist will carefully ask the subject about metal within the subject's body (this includes certain dyes found in tattoos). If there is any question about potentially hazardous metal within the subject's body, we will be excluding the subject from participation in this research study. We will also keep the exam room locked so that no one carrying metal objects can enter while the subject is in the scanner.

The study involves entering a large room in which a magnet is present. The subject will be placed on a narrow bed and then slid into a small tunnel approximately 6 feet in length and 25 inches in diameter. The subject will be asked to lie still for about one hour on this bed. The subject will hear a loud machine-like noise. The subject may be asked to have a harmless monitoring device applied during the study. During the study, the subject can have voice contact and physical contact with someone in attendance if desired.

1.3.3 Standard dose CT (SDCT) Risk

SDCT is a standard medical procedure in lung imaging, widely used clinically and in research. Risks to participants are minimal. The study will involve a small amount of radiation exposure to the subjects. There will be one SDCT scan performed during the study. The scan protocol will be adjusted based on the participant weight. The average weight adult radiation dose is 4 mSv per scan, (8mSv) for the study. This compares to the US limit on radiation workers which is 50 mSv. Risk: The SDCT (lung scan) will be reviewed by a qualified person. There is a possibility that while reviewing the SDCT an incidental finding will be identified.

Managing risk: The patient will be informed about the incidental finding. With permission from the patient, the information about the incidental finding will be forwarded to the primary doctor or the patient can be referred to an appropriate doctor for further evaluation.

The patient will be provided the following information:

- An incidental finding may cause you to feel anxious.
- Since an incidental finding will be part of your medical record, it may affect your current or future life or health insurance coverage. This risk will vary depending on the type of insurance plan involved.

CONFIDENTIAL

This document is confidential and the property of the Duke University.

- The costs for any care that will be needed to diagnose or treat an incidental finding would not be paid for by this research study. Any additional tests or treatments will be your choice; you or your insurer will be responsible for additional costs.

1.3.4 Risk of Incidental Findings

Since the MRI methods being tested are experimental, the MRI images will not be formally reviewed for incidental findings. However, if there is something that is of concern to the PI, then the PI will approach the IRB for guidance on how to proceed on a case-by-case basis. The consent will clearly state that the MRI images will not be evaluated for incidental imaging findings.

1.3.5 Protection Against Risk:

1. Subjects will stay on their prescribed oxygen levels while participating in the study. Oxygen will be discontinued briefly for 2 preparatory breaths prior to xenon inhalation, and then re-started after that.
2. Each subject will be allowed to read the consent form and ask questions. After all, the study subject questions are answered, and before any protocol-specified procedures are initiated, each subject will sign and date the consent form. A copy of the signed consent will be provided to the subject
3. Every effort will be made to keep your information confidential; however, this cannot be guaranteed
4. Duke University has formal education and certification procedures regarding research ethics (<https://irb.duhs.duke.edu/training-and-education>). All research personnel will complete these in full before entry into the protocol; the study's nature and risks will be reviewed with each subjects.

2 Study Objectives

The proposed research builds on the established sensitivity of Hyperpolarized ¹²⁹Xe MRI to obstructive (Ebner'17, restrictive (Rankine'20) and pulmonary vascular lung disease (Wang '19), features expected to be represented in the Covid-19 cohort. It further incorporates new understand of the possible role of myocardial injury in these recovered patients by combining cutting edge pulmonary and cardiac MRI.

Although the initial presentation of patients with moderate to severe symptoms of COVID19 infections is dominated by respiratory symptoms, 10% go on to develop persistent post-infection symptoms which are thought to have an inflammatory etiology. Evidence suggests that pathologic activation of the inflammasome persists beyond the acute initial presentation that contributes to the persistent disabling symptoms characterized as “long-haul COVID”. For this trial, subjects will be eligible for enrollment if they are outpatients with a history of a laboratory confirmed diagnosis of COVID-19 infection, and after 60 days or longer. We will enroll 13 subjects who continue to have respiratory symptoms (i.e., cough, shortness of breath, dyspnea on exertion). An additional 10 subjects engaged in competitive sports and diagnosed with COVID-19 will also be enrolled. These subjects can be asymptomatic or mildly to moderately. Although rare, cardiac impairment has been documented in <2% of these

CONFIDENTIAL

This document is confidential and the property of the Duke University.

individuals. To our knowledge, XeMRI has not yet been studied in this specific patient subset.

The 6-minute walk test and PFTs will not be used to guide enrollment, but rather will be used in combination with XeMRI/cMRI to assess degree of functional impairment. We will stratify our results based on ethnicity and spirometric abnormalities from those subjects without these findings.

Existing data highlight significant racial and ethnic disparities with historically underserved minority populations (i.e., Black, LatinX) suffering disproportionately higher infection rates and more severe illness compared to Whites. This is reflected by the population enrolled in our RedCAP database and biorepository. As such 30% of subjects enrolled will be required to be from underserved communities.

2.1 Primary Study Aims

- Aim 1 - Determine the cardiopulmonary structure-function abnormalities that characterize early phase COVID-19 recovery. We anticipate conducting ¹²⁹Xe and cardiac MRI in 13 recovering COVID patients recruited at their clinic visit 60 days' or longer post-discharge from their acute infection. We will recruit patients with new onset persistent and continued dyspnea and to characterize the interstitial, pulmonary vascular and myocardial abnormalities relative to a control population.
- Aim 2 – Characterize the evolution of cardiopulmonary abnormalities over 9 months. Patients will undergo repeat scanning 9 months later to assess changes in all regional parameters acquired from pulmonary and cardiac MRI, directly addressing the possible reversibility of cardiopulmonary limitations arising from “long COVID.”
- Aim 3 – Identify MRI features that predict physiologic outcomes and can alter treatment decisions. Patients will undergo PFTs and quality of life evaluations at 3, 6 and 9 months, as well as detailed clinical histories. These data will be used to understand which baseline imaging features are predictive of long-term quality of life and physiology outcomes as well as those that represent “treatable traits” that can be targeted for therapeutic intervention.

3 Study Design

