Statistical Methodology	
¹²⁹Xe MRI metrics will include RBC/barrier, barrier/gas, RBC/gas and several spectroscopic indices. Continuous data will be presented using the mean \pm SD if normally distributed and median with 25th and 75th percentiles otherwise. We are fortunate to be able to compare the findings in our images to a database of approximately 30 healthy reference subjects whom we have scanned to date. These subjects have undergone the same ¹²⁹Xe MRI protocol and were recruited with no histories of smoking or cardiopulmonary disease, FEV1>80%, FEV1/FVC>0.70 and DLCO>80%. For subjects to be included in the reference cohort they further had an RBC/barrier ratio \geq0.45 (at TR=15 ms), and image SNR >5, based on the Rose criterion. Comparisons between these groups will use analysis of variance (ANOVA0 methods or Kruskal-Wallis test as appropriate.

-------------------------	---

CONFIDENTIAL

This document is confidential and the property of the Duke University.

1 Introduction

The next phase of the COVID-19 pandemic is likely to see a surge in associated chronic cardiopulmonary disease that will challenge health systems. Recovered patients are presenting with persistent dyspnea at our Duke Pulmonary Post-COVID clinic. Evidence is now mounting that recovered patients have significant residual pulmonary disease, while myocardial injury has also been increasingly reported. To optimally care for these patients, we must comprehensively assess and monitor the changes in cardiopulmonary function and relate them to physiologic and quality of life outcomes. We will deploy cutting edge MRI to fully characterize cardiopulmonary function in enrolled 23 subjects post recovery and 6-9 months later. Cardiac MRI will assess myocardial status and right ventricular function, while hyperpolarized ^{129}Xe MRI will provide 3D assessment of pulmonary ventilation, interstitial barrier integrity and pulmonary vascular hemodynamics. The overall objective outlined in this study is to demonstrate feasibility and value of comprehensive longitudinal imaging characterization of cardiopulmonary structure and function in patients recovered from Covid-19.

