4.3 Subject Recruitment and Screening

Potential subjects will be identified in the Duke post-COVID clinic by clinical staff at their standard of care (SOC) at 6-12 wks. after their initial COVID-19 diagnosis. The clinical staff will focus on identifying subjects with persistent and continued dyspnea after COVID-19 infection. At initial SOC visit (post-diagnosis of COVID positive), subjects will undergo evaluation in pulmonary clinic. Pulmonary function testing (PFTs) 6-minute walk test (6MWT), and relevant labs will be ordered as indicated by the pulmonary physician. Subjects will be invited to participate in the post-COVID Pulmonary Biorepository and the COVID Long-Haulers pilot study. A subject can enroll in the COVID Long Haulers pilot without enrollment in the Biorepository.

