6.1 Study Visits

Potential subjects will be identified in the Duke Post-COVID at their SOC visit after their initial COVID-19 diagnosis. At the subject initial SOC visit, if indicated, subjects may undergo SOC pulmonary function testing, 6-minute walk test, laboratory blood testing, chest X-ray and cardiac MRI. Subjects will undergo ¹²⁹Xe MRI at the baseline visit and ¹²⁹Xe MRI and cardiac MRI at the 6-9-month visit.

CONFIDENTIAL

This document is confidential and the property of the Duke University.

6.2 *Scheduled of Event*

1 For women of childbearing will be performed prior to The test must be negative will be conducted and who have completed Duke Office of Clinical

2 An MRI screening form will session and verified before MRI is performed on a session, the subject will need form for each imaging

3 The ¹²⁹XeMRI session will be MRI scanner. Hyperpolarized the study team. During MRI professional (MD, DO, PA, to monitor subjects during related to Xenon MRI.

4 The Cardiac MRI session will Cardiovascular Magnetic

5 Based on the known additional effects are released from the imaging

6⁷. These procedures are considered the standard of care

8 The Research Cardiac MRI will be conduct during visit 2, will use Dotarem (IV contrast) 0.15 mmol/kg.

Protocol Activities	SOC Visit Baseline (V0)	SOC Visit Visit 1 (V1)
Months	Post COVID	6-9 Months
Informed Consent	X	
History re: Disease, exposure, secondary diagnoses	X	X
Medical history	X	
Concomitant Medications ⁶	X	X
Pregnancy Test (serum/urine) ¹	X	X
Pulmonary Function Testing with DLCO ⁶	X	X
Labs ⁷	X	X
6MWT ⁷	X	X
MRI Screening ² Form	X	X
Imaging Session (Cardiac MRI) ⁴	X ⁷	X ⁸
Imaging Session (¹²⁹ Xe MRIs) ³	X	X
Adverse Events ⁵		X
Standard dose CT	X	X
Vital Signs Assessment with optional noninvasive, optical Hemoglobin measurement	X	X

potential, a serum pregnancy test the cardiac and ¹²⁹XeMRI studies. before the MRI. The pregnancy test interpreted by study personnel competency training from the Research (DOCR).

be completed at the screening starting the imaging session. If an different day from the screening to complete a new MRI screen session.

conducted on the CAMRD research ¹²⁹Xe is produced and delivered by session, a qualified medical LNP, RN, RT, or MT) will be on hand MRI and note any symptoms

be conducted at the Duke Resonance Center (DCMRC). pharmacokinetics of Xenon, no expected after the subject is study.

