6.2.2 Baseline (V0) (post COVID DX)

Informed consent will contain a statement that indicates that if a subject does not qualify to continue in the research study after the end of the screening, he/she will be withdrawn from

the study. Subjects that sign consent but do not pass the screening are considered enrolled in the research study and counted as withdrawn.

- After obtaining informed consent, the following data may be collected and documented on the source (paper or subject's electronic medical record):
 - Documentation of relevant patient history and symptoms – SOC
 - Medical History (including comorbid conditions) – SOC
 - Vital signs (temperature, heart rate, blood pressure, respiratory rate, and pulse oximetry) including weight and height - SOC
 - Including optional noninvasive, optical hemoglobin measurement
 - Concomitant Medications – SOC
 - PFT's - SOC
 - 6MWTs – SOC
 - Labs- SOC
 - Chest X-ray-SOC
 - MRI Imaging -SOC
 - Cardiac MRI
 - Completion of MRI screening form - research
 - MRI Imaging session – research
 - ^{129}Xe MRI
 - Urine pregnancy test (if applicable) performed outside the 48hrs window
 - Adverse event reporting – research
 - Standard dose CT - research

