6.2.3 Visit 1 (V1) (6-9 months)

The following data may be collected and documented on the source (paper or subject's an electronic medical record):

- Documentation of relevant patient history and symptoms – SOC
- Medical History (including comorbid conditions) – SOC
- Vital signs (temperature, heart rate, blood pressure, respiratory rate, and pulse oximetry) including weight and height - SOC
 - Including optional noninvasive, optical hemoglobin measurement
- Concomitant Medications – SOC
- PFT's - SOC
- 6MWTs – SOC
- Completion of MRI screening form - research
- MRI Imaging session – research
 - Cardiac MRI
 - ^{129}Xe MRI
- Serum Pregnancy testing for a female of childbearing potential - research
 - Urine pregnancy test (if applicable) performed outside the 48hrs window
- Adverse event reporting – research
- Standard dose CT - research

CONFIDENTIAL

This document is confidential and the property of the Duke University.

7 Statistical Plan

7.1 *Sample Size Determination*

Power calculation: Based on the ^{129}Xe MRI metrics from our study (Wang, et al., 2019), we expect that we could detect an absolute difference of high barrier uptake of 10% between the post-COVID subjects and an existing cohort of healthy controls. We assume that with a standard deviation of 10% high barrier uptake within patients, and requiring a power of 90%, that a two-sided test would require a sample size of 23 to detect a difference. However, given that high-barrier uptake is expected only in the post-COVID group, a one-sided test suggests the proposed sample size has 99% power to detect a significant difference.

7.2 *Statistical Methods*

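### Aim 3 promises quality-of-life and lung-function evaluations at 3, 6 and 9 months, but section 6 schedules no quality-of-life assessment and only one follow-up visit

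*Combined protocol and SAP*

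**What the plan says.** Section 2.1, Aim 3: "Patients will undergo PFTs and quality of life evaluations at 3, 6 and 9 months, as well as detailed clinical histories". The same aim gives the purpose, which is to learn "which baseline imaging features are predictive of long-term quality of life and physiology outcomes". The Introduction (section 1) sets a matching goal for the changes in cardiopulmonary function: to "relate them to physiologic and quality of life outcomes".

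Section 6 has two visits. Section 6.1 and the schedule of events in 6.2 give V0 and one visit at 6-9 months. Section 6.2.2 lists the V0 items and section 6.2.3 the V1 items.

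PFTs appear at both visits as standard of care. For the first of them, section 6.1 says: "At the subject initial SOC visit, if indicated, subjects may undergo SOC pulmonary function testing". The V0 list is itself permissive: "After obtaining informed consent, the following data may be collected and documented on the source". The V1 list opens in the same way.

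Two statements bear on when V0 falls. Section 4.3 places recruitment at the clinic visit under "standard of care (SOC) at 6-12 wks. after their initial COVID-19 diagnosis". Section 2 makes outpatients eligible with a history of "laboratory confirmed diagnosis of COVID-19 infection, and after 60 days or longer".

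**The concern.** The aim and the schedule cannot both be followed. Quality of life is one of the two kinds of long-term outcome that Aim 3 wants baseline imaging to predict, yet nothing in section 6 tells the site to measure it. Patient-reported data that are not collected at the time cannot be rebuilt later from images or charts, so the gap would be permanent for each subject already seen.

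For PFTs the loss is partial. There is still a value to analyse at V1, but two visits cannot supply three time points. Because the initial PFT depends on clinical indication, some subjects may also have no V0 value. Any analysis of V1 PFT that adjusts for V0 would then lose those subjects.

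**Working it through.** The plan gives no figure of its own to reproduce here. The check compares what is promised with what is scheduled.

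**1. Quality of life.** The term occurs three times in the document: once in section 1 and twice in Aim 3. It does not occur in section 6 or in section 7 (Statistical Plan), and no instrument is named. Scheduled: 0 of 3 time points.

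**2. Could the gap come from the PDF conversion or from a visit described elsewhere?**
- The schedule table is damaged, but its activity rows are readable and none concerns quality of life. The separate prose lists in 6.2.2 and 6.2.3 have no such item either.
- Footnote 8 to the table mentions a visit 2. Its mark sits in the V1 column and there is no V2 column or section, so it most likely means the second visit, V1.
- The end-of-study telephone call in 4.4.2 is for withdrawn subjects and concerns their safety and well-being. It is not an outcome assessment.
- The history-and-symptoms item is not a substitute, because Aim 3 names clinical histories in addition to quality of life.

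**3. PFT time points.** Aim 3 does not say whether months run from diagnosis, discharge or V0.
- Timing of V0 after diagnosis, at 30.4 days per month: 6-12 weeks = 42-84 days = 1.4-2.8 months; 60 days = 2.0 months, with no upper limit stated. V0 may or may not be the 3-month point.
- A single V1 in a 6-9 month window can be the 6-month or the 9-month point for a given subject, not both.
- Months counted from V0: at most 1 of 3 covered (V1 only).
- V0 read as month 3: at most 2 of 3 covered (V0 and V1).

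**4. As numbers of evaluations.** Section 2 describes 13 symptomatic subjects and 10 in competitive sports, 23 in all. Aim 3 does not say which of these it covers.

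| | 23 subjects | 13 subjects |
|---|---|---|
| Promised per outcome | 23 × 3 = 69 | 13 × 3 = 39 |
| Quality of life scheduled | 0 | 0 |
| PFT, months from V0, at most | 23 × 1 = 23 | 13 × 1 = 13 |
| PFT, V0 as month 3, at most | 23 × 2 = 46 | 13 × 2 = 26 |

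These are multiples of the time-point counts and carry no further information. The documents give no rate of V0 PFTs not done, so no number is put on that loss.

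**5. A looser mismatch.** Aim 2 puts repeat scanning at 9 months, while sections 1 and 6 allow 6-9 months. The window includes 9 months, so this is secondary.

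**The case against.** The strongest reply is that section 6 is not an exhaustive list of what will be collected. The table and the prose lists disagree with each other on several items: labs are marked at V1 in the table but absent from 6.2.3; a chest X-ray is in 6.2.2 but has no table row; adverse events and medical history are placed differently. Both lists use permissive wording. If they omit things the study does elsewhere, absence from them shows only that quality of life is not specified. In the same way, PFTs are standard of care, so clinic tests near 3 or 6 months could sit in the medical record, which is an allowed source. The study is also a 23-subject pilot powered on high barrier uptake, and Aims 1 and 2 do not need quality of life.

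Part of this stands. The PFT counts describe scheduled study visits, not everything that might be retrieved from charts. The V0-adjusted analysis is not one the plan specifies, so the loss of subjects from it is conditional. V1 PFTs are standard of care too and could also be missing.

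The core is not answered. On the two matters at issue, the number of visits and the absence of quality of life, the table and both lists agree. An outcome of a primary aim that rests on an unnamed instrument and an unscheduled assessment has no source in the plan as written. Chart retrieval may recover some PFTs, but nothing in the plan would place a quality-of-life questionnaire in the chart.

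**Conclusion.** The concern holds. This is a contradiction between a primary aim and the schedule, not merely missing detail. Quality of life has 0 of 3 promised time points on every reading. PFT has at most 1 of 3 or at most 2 of 3, depending on a time origin that the plan does not state. The counts assume that section 6 is followed as written and that visit 2 in footnote 8 means V1.

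The damage is confined to Aim 3: its quality-of-life part cannot be answered, and its physiology part is thinner than promised. Aim 1 and the sample-size calculation in 7.1 are not affected. It should be corrected, ideally before enrolment, because missed quality-of-life assessments cannot be recovered.

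**What to change.** Reconcile Aim 3 with section 6 by one of three routes.

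1. **Preferred.** Add one named quality-of-life questionnaire at V0 and V1 in the 6.2 table and in 6.2.2 and 6.2.3. Reword Aim 3 so that its outcomes are quality of life and PFT at V1, in place of the three time points. Add a sentence to 7.2 on how each will be related to baseline imaging. Analyse V1 PFT in all subjects who have it; adjust for V0 PFT in the subset with a V0 value and report the size of that subset. Cost: wording, plus the time to complete a questionnaire at two existing visits (likely a few minutes, depending on the instrument chosen). Downside: fewer time points than Aim 3 now promises.
2. **Schedule what is promised.** Add the 3, 6 and 9 month assessments to section 6, still with a named instrument. Cost: extra visits or remote contacts.
3. **Withdraw the claim.** Delete quality of life from Aim 3 and section 1, and match the PFT time points to V0 and V1. Cost: wording only, but the quality-of-life question is given up.

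The preference for route 1 rests on cost. The documents do not settle which the sponsor intended.

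Under any route, state the time origin (diagnosis, discharge or V0) and whether Aim 3 covers 13 or 23 subjects. As a secondary tidy-up, align Aim 2 with the 6-9 month visit and record actual months since baseline, for use as a covariate in any analysis of change.
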